### **C. Study Design and Research Methods:**

1. Prescreen FDRs by phone for ability to participate and lack of MS symptoms, using a standardized script to exclude those with overt MS symptoms. Proband MS patients will have documented MS by McDonald 2017 criteria.
2. Qualified FDRs will be scheduled for a study visit after completing a pre-screening questionnaire by phone. If they are not excluded by pre-screen, and wish to participate, a study visit will be scheduled. A waiver of documentation of consent will be obtained over the phone so as to instruct participants to fast from midnight prior to the first study visit. This will also allow them to fill out the environmental questionnaire on-line before their visit and at their convenience. The environmental survey must be completed at least three days prior to their visit. If not, the study visit will be canceled and rescheduled once its complete.
3. A study visit will include (See Table of activities below):
  - a. Read, ask questions regarding, and sign the consent.
  - b. Document completion of environmental questionnaire.
  - c. Obtain a measured height and weight, and compute a Body Mass Index (BMI)
  - d. Perform a non-contrast brain MRI (per section V.A)

- e. Perform a fasting Blood draw consisting of no more than 100 ccs of blood.
  - i. Blood drawn at the primary study visit will be a maximum of 100 ccs to be processed in the following fashion. Participants will not be made aware of their blood sample results
    - 1. 30 ccs for immediate cell sort by [name] into T and B lymphocytes, for CD40 expression studies, requiring primary analysis with fresh cells, and done on all samples. Also for HLA analysis.
    - 2. 20 ccs processed for delayed analysis of SNPs, viral serologies (Herpes Simplex Virus 1 and 2, Cytomegalovirus, Varicella-Zoster Virus, and Epstein-Barr Virus), vitamin D levels, and neuroaxonal (NfL - Quanterix) and myelin damage (lipids), which all can be performed on stored samples.
    - 3. 50 ccs processed and stored for delayed analysis of plasma and PBMCs, RNA and DNA, for studies not yet determined
- f. Perform the Perceived Stress Scale and the Neuro-QoL screen for anxiety and depression;
  - i. Participants screening for concerns for suicidality on the mood screen will be referred to an emergency room for evaluation.
- g. Perform a Symbol Digit Modality Test, a screen for cognitive function. The latter will be done in the written format.

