  - i. Participants will not be advised of Cognitive screen results.
- h. As a measure of physical activity, we will use Godin Leisure-Time Exercise Questionnaire (GLTEQ), which measures mild, moderate and strenuous physical activity during a typical seven day period. This has been validated in MS, and is scored either into three levels of activity (sedentary, moderately active, or active), or may be used as a continuous measure.
- i. As a dietary assessment, we will use the Harvard 2007 Booklet FFQ, which is a semi-qualitative food frequency questionnaire used to assess intake of various nutrients over the past year. This has been robustly validated in a variety of populations, and nutrient intakes are computed by assigning a daily frequency weight.

4. MRIs will be read by a board-certified neuroradiologist ([name]) with extensive experience in reading brain MRIs in general, and MS MRIs in particular. All FDRs will receive a follow-up contact concerning the results of their MRI within one week. FDRs with a brain MRI fulfilling criteria for DIS will be referred to a qualified neurologist to determine if they should be treated or monitored more closely. Individuals with abnormal brain MRI scans not suggestive of or fulfilling DIS criteria, but having non-specific brain lesions (as can be seen with migraine and many other conditions), also will be referred to a qualified neurologist for evaluation as needed. Those FDRs with unexpected abnormalities (e.g. severe sinus disease, pineal cyst, pituitary abnormality, cavernous angioma, etc.) will be referred as necessary to a qualified physician.

5. FDRs with a positive brain MRI showing lesions DIS will be asked to return within four months for a repeat blood draw of no greater than 100 cc of blood, to be compared to age-and sex-matched FDRs without a positive brain MRI (who will also be asked to return within 4 months for the repeat blood draw) and age-and sex-matched non-FDRs, both in a 1:1 ratio. The former will be identified from those already in the study, and the latter will be recruited from age- and sex-matched friends of the FDRs with positive brain MRIs. The non-FDRs will be prescreened and perform all the study procedures as the FDRs on the first study visit, with the exception of the MRI.

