- a. This blood draw will be for B cell anergy and cytokine studies in [name] lab, and repeat CD40 studies on non-FDR controls (i.e. not already done by [name] lab) which require fresh cells, but done only on this subset of participants. The rest of the blood will be processed and stored as described in C3ei.3 above for potential future use.

6. Data will be stored in a HIPAA-compliant database. Analysis will be done via case-cohort approach with the roughly 15-30 MRI-positive participants, controls as noted, and looking at the markers individually and together.

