## STUDY PROCEDURES

		Visit 1	Visit 2 (within 4 months after V1)
FDRs	MRI positive	Vitals MRI Blood draw Environmental Questionnaire NeuroQOL SDMT Activity Questionnaire Diet questionnaire	Blood draw
	MRI negative Controls	Vitals MRI Blood draw Environmental Questionnaire NeuroQOL SDMT Activity Questionnaire Diet questionnaire	Blood draw
	MRI negative Non-Controls	Vitals MRI Blood draw Environmental Questionnaire NeuroQOL SDMT Activity Questionnaire Diet questionnaire	
NonFDR Controls		N/A	Vitals Blood draw Environmental Questionnaire NeuroQOL SDMT Activity Questionnaire Diet questionnaire

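### Within each matched set, CD40 in the non-FDR control is always assayed after the case and never alongside it, and no adjustment for assay date or lot is planned

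*Combined protocol and SAP*

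**What the plan says.** Section V.C.3.e assigns part of the Visit 1 blood to an immediate cell sort "for CD40 expression studies, requiring primary analysis with fresh cells, and done on all samples". That is the only CD40 measurement the protocol gives to FDRs.

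Section V.C.5 brings DIS-positive FDRs and their matched DIS-negative FDRs back within four months. Of that draw, V.C.5.a says "This blood draw will be for B cell anergy and cytokine studies" and adds "repeat CD40 studies on non-FDR controls", explaining that these are the people in whom CD40 has not yet been done. "The rest of the blood will be processed and stored" for possible later use.

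For non-FDRs, V.C.5 says "The non-FDRs will be prescreened and perform all the study procedures as the FDRs on the first study visit, with the exception of the MRI". The Study Procedures table marks their Visit 1 as not applicable and puts all their procedures in the column headed "Visit 2 (within 4 months after V1". V.C.5 recruits them as friends of MRI-positive FDRs; V.B also allows recruitment from neurology offices.

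Section V.F plans a comparison of cases with both control groups. Neither V.C nor V.F mentions CD40 assay date, reagent lot, a reference sample or any adjustment for them.

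**The concern.** A fresh-cell assay cannot be batched at the end of the study, so a side-by-side comparison that is missed at the visit cannot be recovered from stored samples. Here the order of assay is fixed by group: case first, non-FDR later. If reagents, instrument settings or operators change over time, part of an apparent difference between DIS-positive FDRs and non-FDRs may come from the laboratory, and a true difference may be hidden.

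CD40 expression on T cells is one of the two immunological markers that section III puts forward as possibly present in FDRs. The second draw already supplies fresh blood from all three members of each set, yet CD40 is named for only one of them.

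**Working it through.** The documents give no CD40 effect size, assay variation, accrual length or definition of a run, so there is no stated figure to reproduce. Assumptions are marked as such.

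**1. Visit and group.** All case values come from Visit 1 and all non-FDR values from the Visit 2 slot. For case v non-FDR, a model with intercept, group and visit has rank 2 of 3: group and visit label cannot be separated. A CD40 value from cases at the second draw would bring the rank to 3.

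**2. Calendar time.** Visit label is not the same as assay date. Assume 300 FDRs accrue evenly over T months and each non-FDR is drawn 0.25 to 4 months after its case's Visit 1 (upper limit from the table heading). Simulation gives:

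| T (months) | Non-FDR draws while FDR Visit 1 assays continue | Correlation of group with date (size) | Variance inflation |
|---|---|---|---|
| 6 | 64% | 0.50 | 1.34 |
| 12 | 82% | 0.29 | 1.10 |
| 24 | 91% | 0.16 | 1.03 |
| 36 | 94% | 0.10 | 1.01 |

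Group and date overlap enough to be separated, provided that the date is recorded and used.

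**3. Size under rolling draws.** With linear drift totalling D SD over T months, the mean shift between case and non-FDR is D x mean lag / T, where the mean lag is (0.25 + 4)/2 = 2.125 months. The rejection rate is that of a two-sided 5% two-sample t-test with noncentrality shift / sqrt(2/n), n = 30 per group:

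- T = 12, D = 1: shift 2.125/12 = 0.18 SD, about 10%.
- T = 12, D = 0.5, or T = 24, D = 1: shift 0.09 SD, about 6%.
- T = 24, D = 0.5: shift 0.04 SD, about 5%.
- T = 36, D = 0.5 to 1: shift 0.03 to 0.06 SD, 5-6%.

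At 15 v 15 the largest of these (0.18 SD) gives about 8%. Random lot shifts with SD 0.5-1 have no fixed direction; adding them to the simulation gives an overall range of about 3-10% at 30 v 30. Rates below 5% arise because a case and its control often share a lot, which an unpaired test ignores.

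**4. Size if non-FDRs are a late block.** If all were assayed at the close of accrual, half the drift would lie between the average case and the block: 0.25 SD for D = 0.5 and 0.5 SD for D = 1. By normal approximation this gives 16.2% and 49.1% at 30 v 30, and 10.5% and 27.8% at 15 v 15. Simulation with linear drift or lot shifts gives about 17-64% at 30 v 30.

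**5. Effect of adjustment.** DIS-negative FDRs number 300 - 30 = 270 to 300 - 15 = 285, so the time course of the assay is well estimated from FDRs alone. Adjusting for assay date or lot with all FDR values returns the simulated rate to about 4-7%. One limit applies: if a late block fell wholly within lots that no FDR shares, lot and group would be aliased and no adjustment for lot could be fitted.

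**The case against.** The best defence is that cells are sorted on arrival and non-FDRs are recruited around individual cases, so their assays would fall among the Visit 1 assays of other FDRs. For a non-FDR the Visit 2 slot is a first and only visit under first-visit procedures. Aim 2 concerns DIS among FDRs, the case v DIS-negative FDR contrast is Visit 1 v Visit 1, and V.F already calls the pilot underpowered and imprecise. All of this stands, and it limits the size of the problem. It does not remove it, because overlap in time helps only if the date is recorded and used in the analysis, and the plan provides for neither.

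Two stronger readings are tempting. A reader might infer that group is fully confounded with assay run and that no FDR sample shares a run with a non-FDR. The documents define no run and do not say that non-FDRs are held back as a block; step 2 points the other way under rolling accrual. A reader might also infer that a CD40 request at Visit 2 reveals the group to the laboratory. The protocol does not say what a request shows, so that is conjecture; all that can be said is that no masking of the laboratory is described.

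A third objection concerns the remedy. Repeating CD40 in cases at Visit 2 and making those values the main comparison could bring in a new bias: V.C.4 refers cases after MRI for a decision on treatment or monitoring, so some might be treated before the second draw. This stands, and the fix allows for it.

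**Conclusion.** The ordering is in the text: within every matched set the non-FDR's CD40 is measured after the case's, never concurrently, and the plan offers no means of separating drift from group. The consequence for the case v non-FDR contrast is a false-positive rate of about 3-10% at 30 v 30 when draws are rolling, and about 17-64% only under a late block. These figures rest on assumed drift (0.5-1 SD in total, or lot shifts with SD 0.5-1), accrual of 12-36 months and the assumed lag; none of these is in the documents apart from the four-month window. The contrast between cases and DIS-negative FDRs does not share this ordering. This is a modest weakness with a remedy that costs no assays, not a flaw that invalidates the CD40 work.

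**What to change.** 1. Record CD40 assay date and reagent lot for every participant (V.C.3.e and V.C.5.a).
2. In V.F, state that the case v non-FDR CD40 analysis adjusts for date and lot using the CD40 values of all FDRs, including the roughly 270-285 who are DIS-negative. Keep age and sex in the model, since using all FDRs goes beyond the matched sets.
3. Draw non-FDRs while FDR accrual is still open, so that dates and lots overlap.
4. Optionally, repeat CD40 on the already planned Visit 2 sample of the matched DIS-negative FDRs as a bridge. Keep the cases' Visit 1 values as the main comparison.
5. Reword "repeat CD40 studies on non-FDR controls" as a first CD40 assay in non-FDRs.

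Items 1, 2, 3 and 5 cost record-keeping, scheduling and analysis time only. Item 4 costs 15-30 assays, one per matched DIS-negative FDR, with no additional blood draw.

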The sequences were specifically chosen to: a) screen brain with the greatest specificity (FLAIR\*); b) allow for later volumetric analysis of the brain; and c) use the most sensitive technique for cortical and subcortical brain lesions (3D-DIR).

**B. Description of Population to be Enrolled:** The population will be a total of 300 women and men, of all races and ethnicities, between the ages of 18-30, inclusive, who have no symptoms of MS, but have at least one FDR with documented MS fulfilling McDonald 2017 criteria. Up to 1000 will be screened for inclusion, but some will be excluded due to inability to undergo a brain/spine MRI or have blood drawn, lack of interest after discussion of study requirements, or symptoms concerning for MS (the latter will be referred to a qualified neurologist for evaluation). FDRs with one or more siblings/parents with MS will be included, and more than one FDR of a proband MS patient will be allowed. A control group (based on # of FDRs with positive MRIs - we anticipate 15-30) of age- and sex-matched controls who have no known family members with MS (out to first cousins and grandparents) will have blood drawn and fill out the environmental questionnaire, but will not undergo a brain MRI. The controls will be matched 1:1:1 for those FDRs with positive MRI scans suggesting pre-symptomatic MS and those age-and sex-matched FDRs who do NOT have positive MRI scans suggesting pre-symptomatic MS. The ages were specifically chosen so as to have a good opportunity to collect an adequate number of MRI-positive, asymptomatic participants prior to the known median age of MS clinical onset (30 years), but not so young as to lower the likelihood of detecting asymptomatic brain MRI lesions.

1. FDR Inclusion Criteria
  - a. Male and female
  - b. All races and ethnicities
  - c. Ages 18-30
  - d. Must have a parent, sibling or child with MS fulfilling McDonald 2017 criteria
  - e. No symptoms suggestive of MS on formal screen
  - f. Ability to undergo a non-contrast MRI and venipuncture, and perform an environmental screen, mood screen and cognitive test
2. FDR Exclusion Criteria
  - a. Symptoms suggestive of MS on formal screen
  - b. Prior diagnosis of autoimmune disease that may be associated with CNS dysfunction and MRI lesions, e.g. Sjogren's
3. Non-FDR Inclusion Criteria
  - a. Male and female
  - b. All races and ethnicities
  - c. Ages 18-30

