  - d. Must NOT have a FDR (parent, sibling, child) or second degree relative (grandparent, aunt or uncle) with MS fulfilling McDonald 2017 criteria
  - e. No symptoms suggestive of MS on formal screen
  - f. Ability to undergo venipuncture and perform an environmental screen.
4. Non-FDR Exclusion Criteria
  - a. Symptoms suggestive of MS on formal screen
  - b. Prior diagnosis of autoimmune disease that may be associated with CNS dysfunction and MRI lesions, e.g. Sjogren's

FDR participants will be enrolled from among the FDRs of MS patients seen at the Rocky Mountain Multiple Sclerosis Center at the University of Colorado in Aurora, Colorado (RRMSC at CU). Our center has approximately 3500 unique patients, of whom nearly all have asymptomatic FDRs, many in the appropriate age range. Documented MS proband patients will be made aware of the study via interactions in the office, our newsletter, and IRB-approved information given to them for their FDRs. FDRs who are then interested will initiate contact with the research group. If this does not provide adequate enrollment, we will recruit by local advertisement through known offices of neurologists in the Denver and surrounding regions. Age- and sex-matched non-FDR controls will be recruited from the friends of FDRs who are positive on the screening MRI, or will be recruited from local recruitment in the department of Neurology offices, from those non-MS conditions. FDRs and controls will be screened on the phone for basic demographic criteria (e.g. age, location where they live) and a checklist of basic MS symptoms, and to be certain they do not have previously undiagnosed MS or other autoimmune/neoplastic disorders. Those with concerns for MS at screening will be referred to a qualified neurologist for assessment.

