## **F. Data Analysis Plan: Statistical Approach**

- a. Based on previous studies, we estimate that 5-10% of the 300 FDRs (15-30) in our pilot study will exhibit an MRI endpoint. In order to test for associations with this endpoint to obtain valuable preliminary data, we will perform a nested case control study. We will match two controls per case based on age and sex: one group will be FDRs not fulfilling DIS on brain MRI; the second will be non-FDRs who are age- and sex-matched to FDRs who do, and do not, fulfill DIS on MRI scans. The non-FDRs will perform the environmental screen and undergo venipuncture for blood analysis identical to the other two groups, but will not have a MRI scan.
- b. Aim 1. Descriptive statistics

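### Section V.C item 6 names a case-cohort analysis and V.F item a a matched nested case-control study for the same data; the sampling described does not fit case-cohort methods

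*Combined protocol and SAP*

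**What the plan says.** All references are to the combined protocol and SAP.

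- **Section V.C, item 6:** "Analysis will be done via case-cohort approach with the roughly 15-30 MRI-positive participants, controls as noted".
- **Section V.F, item a:** "we will perform a nested case control study. We will match two controls per case based on age and sex". One control per case is an FDR who does not meet the criteria for lesions disseminated in space (DIS); the other is a non-FDR.
- **Section V.B:** "The controls will be matched 1:1:1 for those FDRs with positive MRI scans suggesting pre-symptomatic MS", which is the same individually matched structure.
- **Source of FDR controls (V.C, item 5):** "The former will be identified from those already in the study", that is, MRI-negative members of the 300-person cohort.
- **Source of non-FDR controls:** V.C item 5 says "the latter will be recruited from age- and sex-matched friends of the FDRs with positive brain MRIs". The recruitment paragraph of V.B gives friends as one source and adds a second: "or will be recruited from local recruitment in the department of Neurology offices".
- **Model:** V.F item c promises association analyses of single factors and a multiple risk factor analysis. It bases power on 30 cases and 60 matched controls taken together. No section names a regression model, a random subcohort, a sampling fraction or weights, or says how the matched sets will be used.

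**The concern.** The two sections give different design names to one analysis, and the names carry different methods. A case-cohort analysis compares cases with a subcohort drawn at random from the whole cohort without regard to outcome, and it uses the sampling fraction. A nested case-control analysis compares each case with controls chosen for that case from the same cohort, and it accounts for the matching.

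The controls described here are not a random subcohort. The FDR controls are chosen to match cases on age and sex. The non-FDR controls were never members of the FDR cohort, so neither design name covers them.

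The choice of model is therefore open until after the data are seen, and the one phrase in V.C that points towards a method points to one the sampling cannot support. If an analyst followed it and treated matched controls as an unmatched reference group, odds ratios could be understated. The lifestyle factors in the environmental screen would be most exposed to this, because friends may share them.

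**Working it through.** **1. The passages side by side**

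| Feature | Case-cohort needs | Plan provides |
|---|---|---|
| Comparison group | Random subcohort of the FDR cohort | MRI-negative FDRs matched to cases, plus non-FDRs |
| Sampling fraction or weights | Required | None given |
| Membership of the cohort | All | FDR controls only |

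The FDR controls fit a matched nested case-control design. The non-FDR controls are an external matched group.

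**2. The plan's own power figures**

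The plan states 20-33% for single factors (odds ratio, OR, at most 2) and 64% for HLA (OR 2.9). It does not state alpha or exposure frequencies, so two-sided 0.05 is assumed and control prevalence p0 is varied.

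- Case exposure: p1 = OR·p0 / (1 − p0 + OR·p0).
- Power: Φ{[(p1 − p0) − 1.96·√(p̄(1−p̄)(1/30+1/60))] / √(p1(1−p1)/30 + p0(1−p0)/60)}, with p̄ the pooled exposure.
- At p0 = 0.30, OR 2: p1 = 0.4615 and p̄ = 0.3538, so Φ[(0.1615 − 0.2096)/0.1086] = Φ(−0.44) = 32.9%.
- At p0 = 0.10 and 0.20: 21.2% and 29.2%. For OR 2.9 at p0 = 0.28: 64.2%.

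The stated figures are consistent with an ordinary case-control calculation that pools all 60 controls, although two source populations are mixed in them. With one control group only (30 v 30), power at OR 2 is 14.5% at p0 = 0.10 and 24.8% at p0 = 0.30.

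**3. Ignoring age and sex matching (true OR 2)**

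Assume one binary matching factor, cases split evenly over its two levels, and control exposure of 25% at the reference level. Case exposure there is 0.40.

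| OR, exposure v factor | Control exposure, level 2 | Case exposure, level 2 | Crude OR |
|---|---|---|---|
| 1 | 0.250 | 0.400 | 2.00 |
| 1.6 | 0.348 | 0.516 | 1.98 |
| 2 | 0.400 | 0.571 | 1.96 |
| 3 | 0.500 | 0.667 | 1.90 |
| 10 | 0.769 | 0.870 | 1.67 |

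Example for the row at 2: mean control exposure is 0.325 and mean case exposure 0.4857, so the crude OR is (0.4857/0.5143)/(0.325/0.675) = 0.944/0.481 = 1.96.

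**4. Ignoring friend pairs (true OR 2)**

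Assume population exposure p0 = 0.20, so p1 = 0.333, and a case-friend exposure correlation ρ. The documents give no value for ρ.

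- Friend exposure: q = p0 + ρ(p1 − p0).
- Both exposed: P11 = p1·q + ρ√[p1(1−p1)q(1−q)].
- Discordant proportions: b = p1 − P11 and c = q − P11. Paired OR = b/c.
- At ρ = 0.4: q = 0.253, and the crude OR is 0.5/0.339 = 1.47. P11 = 0.0844 + 0.0820 = 0.1665, so b = 0.167 and c = 0.087. The paired OR is 1.92, with 30 × 0.254 = 7.6 discordant pairs.

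| ρ | q | Crude OR | Paired OR | Discordant of 30 | Power, unpaired 30 v 30 | Power, exact paired |
|---|---|---|---|---|---|---|
| 0 | 0.200 | 2.00 | 2.00 | 12.0 | 21% | 13% |
| 0.1 | 0.213 | 1.84 | 1.98 | 11.0 | 18% | 12% |
| 0.2 | 0.227 | 1.71 | 1.96 | 9.9 | 15% | 10% |
| 0.3 | 0.240 | 1.58 | 1.94 | 8.8 | 12% | 8% |
| 0.4 | 0.253 | 1.47 | 1.92 | 7.6 | 10% | 6.5% |

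With 15 pairs, 5.5 to 3.8 are discordant for ρ from 0.1 to 0.4. As a cross-check, a simulation with a shared pair-level tendency to exposure (control prevalence 25%) gave crude ORs of 1.94, 1.80, 1.65 and 1.54 at within-pair correlations of 0.05, 0.16, 0.27 and 0.37.

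**The case against.** The strongest reply is that this is loose terminology. Item 6 of V.C itself points back to the matched controls, so the authors probably mean the matched study of V.F. Neither section states an estimator, and nothing says that matching will be ignored. The example hypothesis in V.F item c compares cases with DIS-negative FDRs of like age and sex, which suggests that matching is meant to count. The plan also calls itself an underpowered pilot with imprecise estimates. At 30 v 30 with 20% exposure, the log OR has standard error √(1/10 + 1/20 + 1/6 + 1/24) = 0.60, so the 95% interval around 2 runs from about 0.6 to 6.5, and a shift from 2.0 to 1.9 is lost in that.

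Much of this stands, and it rules out three stronger readings that a reader might infer:

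- **That the planned analysis is invalid and biased towards 1.** The bias belongs to a procedure that the plan does not describe. It is nil when exposure is unrelated to the matching factors, and for age and sex an unconditional model that adjusts for them also removes it.
- **That all controls are matched on friendship.** The FDR controls come from the cohort and are matched on age and sex. Friendship is a recruitment source for non-FDR controls, one of two in V.B, and no proportion is given.
- **That pairing would recover lost power.** In step 4 the paired analysis restores the OR to 1.92-1.98, but its exact power is lower than that of the unpaired one.

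What does not fall is the conflict itself. Probable intent does not settle which method the plan commits to, and no other section does.

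**Conclusion.** The two sections contradict each other on the design of one analysis. The case-cohort name does not fit the sampling, and the non-FDR group fits neither name. That conclusion rests on the text alone.

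The size of any harm is conditional on matching being ignored. For age and sex, a true OR of 2.0 would appear as 2.0 if exposure is unrelated to them. It would appear as about 1.9 to 1.98 if the association between exposure and matching factor has an OR of 1.6 to 3; only a very strong association does more. For friend controls it would appear as 1.84 to 1.47 if case-friend exposure correlation is 0.1 to 0.4, which is an assumption, and only in the comparison with non-FDRs. Aim 1, a descriptive prevalence, does not depend on the matched sets. The point is worth correcting because it is cheap and closes off a choice of model after the data are seen, not because a biased result has been shown.

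**What to change.** 1. Delete the case-cohort wording from V.C item 6 and use one design description in V.C and V.F: a matched case-control study nested in the FDR cohort, plus a separate external comparison with non-FDRs.
2. For DIS-positive v DIS-negative FDRs, state the model: logistic regression adjusted for age and sex, penalised given 15-30 cases, or conditional logistic regression on the matched sets.
3. For DIS-positive FDRs v non-FDRs, record each control's recruitment source and a matched-set identifier. Keep the pair for controls recruited as friends of a case; adjust for age and sex for those recruited through neurology offices.
4. Report the two control groups separately, and restate power for each rather than for 60 pooled controls.

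The text cost is a few sentences and two stored variables. The statistical cost is real. A paired analysis uses only discordant pairs, about 8 to 11 of 30 under the assumptions above and about 4 to 5 of 15, so its intervals are clearly wider and its power lower than unpaired. Splitting the controls lowers nominal power at OR 2 and 30% exposure from 32.9% to 24.8%. For Visit 1 markers measured in all FDRs, the adjusted model could use every DIS-negative FDR: 30 v 270 gives 44.2% in the same setting, before adjustment.
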